5. On strong opioids with morphine equivalent daily dose of 80-500 mg for at least one week, with stable (i.e. +/- 30%) regular dose over the last 24 hours
6. Karnofsky performance status >/=50%
7. Age 18 or older
8. Able to complete study assessments
Exclusion Criteria
1. Dyspnea at rest >/=7/10 at the time of enrollment
2. Supplemental oxygen requirement >6 L per minute
3. Delirium (i.e. Memorial delirium rating scale >13)
4. History of unstable angina or myocardial infarction 1 month prior to study enrollment
5. Resting heart rate >120 at the time of study enrollment
6. Systolic pressure >180 mmHg or diastolic pressure >100 mmHg at the time of study enrollment
7. History of active opioid abuse within the past 12 months
8. History of allergy to fentanyl
9. Severe anemia (Hb <7g/L) if documented in the last month and not corrected prior to study enrollment*
10. Diagnosis of acute pulmonary embolism within past 2 weeks
11. Diagnosis of pulmonary hypertension
12. Unwilling to provide informed consent

* To minimize study burden for participation in this 2-hour study, extra bloodwork will not be drawn unless the patient already has the above lab abnormalities documented and need to be corrected.

C.3. Study screening. A 2 step consent process will be used. First, a verbal consent will be obtained by the study staff to proceed with screening of potential participants for eligibility and to characterize their dyspnea using the dyspnea survey and the cancer dyspnea scale. Outpatients may be contacted by phone within 1 week prior to their scheduled clinic visit to inform them of this study so they can make necessary arrangements if interested in participating. Eligible patients will then be formally enrolled onto the study after they have signed the informed consent indicating a willingness to participate in the trial. The number of patients screened, approached, eligible, and enrolled will be documented. Reasons for refusal for eligible patients will also be captured.

C.4. Randomization. Patient randomization will be conducted through the Clinical Trial Conduct (CTC) website (<https://biostatistics.mdanderson.org/ClinicalTrialConduct>), which is maintained by the Department of Biostatistics at MD Anderson Cancer Center. The trial statistician will train the users (pharmacists or research nurses) in the use of this website for randomizing patients. The methodology to replace a patient who does

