80-100	200	35.0	43.2	80-130	100	13.5	21.6
101-150	300	35.0	52.0	131-210	200	16.7	26.7
151-200	400	35.0	46.4	211-280	300	18.8	24.9
201-250	500	35.0	43.5	281-450	400	15.6	24.9
251-300	600	35.0	41.8	451-500	600	21.0	23.3
301-400	800	35.0	46.5				

401-500 1000 35.0 43.6 |

* FSS comes in 100 mcg, 200 mcg, 400 mcg, 600 mcg and 800 mcg. A combination of these products would allow us to deliver the desired dose.

The following instructions will be given to the patient:

1. Swallow any saliva in your mouth.
2. Hold the medication spray unit upright using your index and middle fingers and thumb.
3. Point the nozzle into your mouth and under your tongue.
4. Squeeze your fingers and thumb together to spray the medication under your tongue.
5. Hold the medicine under your tongue for 30-60 seconds. Do not spit out any medicine. Do not rinse your mouth.
6. The spray unit will remain locked after use.

C.8. Medication use during study. To minimize the co-intervention effect on dyspnea, patients will be advised to avoid using breakthrough opioids (for any reason) or bronchodilators for at least 2 hours prior to and during the study.

C.9. The Shuttle walk test is an externally paced test, and has been found to be high reproducible for inducing breathlessness in patients with advanced cancer ³¹⁻³³. Furthermore, the shuttle walk test was reported to be equivalent or better than 6 minute walk test in detecting a clinical response ³⁴⁻³⁶. Shuttle walk tests will be conducted according to published procedures ³¹⁻³³. The first shuttle walk test is designed to provide important information regarding a patient's level of dyspnea on exertion, and to facilitate intra-individual comparison since there is significant variability in the expression of dyspnea among patients. The second shuttle walk test will be conducted 10 minutes after study medication has been administered.

The research staff conducting the walk test must be certified in cardiopulmonary resuscitation with a minimum of Basic Life Support by an American Health Association-approved cardiopulmonary resuscitation course. Walking aid is allowed as long as patients keep them the same as before enrollment and during the entire study.

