The shuttle walking test requires the patient to walk up and down a 10 m course. The course will be identified by two cones inset 0.5 m from either end to avoid the need for abrupt changes in direction. The speed at which the patient walks will be dictated by an audio signal played on a tape cassette. The start of the test will be indicated by a triple bleep. Thereafter the tape will emit a single bleep at regular intervals, at which point the subject will attempt to be at the opposite end of the course—that is, by the time the patient heard the signal he should be turning round the cone to proceed back down the course. After a minute on the same level, the subject will proceed to the next level with the speed of walking increased by 0.167 m/s (or 10 m/min). A change of speed to the next level will be indicated by a triple bleep from the tape recorder (Table 4).

To help the patient to establish the routine of the test and the first, very slow, speed of walking, the operator will walk alongside for the first minute. The patient will have 20

seconds to complete each of the three shuttles in the first minute. After this first minute patients will pace themselves to coordinate their walking speed with the timed signals. When patients reached the cone before the signal, they will be instructed to remain until the signal indicated that they could proceed with the test.

Table 4. Shuttle walk test levels

Level	Speed (m/s)	Time required for 10 m course (s)	Number of shuttles per level	Total time in each level (s)	Cumulative distance walked (m)
1	0.500	20	3	60	30
2	0.667	15	4	60	70
3	0.833	12	5	60	120
4	1.000	10	6	60	180
5	1.167	8.57	7	60	250
6	1.333	7.5	8	60	330
7	1.500	6.67	9	60	420
8	1.667	6	10	60	520
9	1.833	5.45	11	60	630
10	2.000	5	12	60	750
11	2.167	4.62	13	60	880
12	2.333	4.29	14	60	1020

The explanation to the patient will be standardized (see appendix). Patients in previous studies found it easy to pace themselves and no difficulties were encountered in administering the test.

The end of the test will be determined by either (a) the patient, when he or she was too breathless to maintain the required speed or (b) the operator, if the patient failed to complete a shuttle in the time allowed (that is, was more than 0.5 m away from the cone when the bleep sounded).

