We will be assessing the dyspnea level with modified Borg scale at baseline and then every minute during at the shuttle walk test as well as at the end. We will also measure the heart rate, respiratory rate, blood pressure, oxygen saturation before and immediate after the shuttle walk test. The total walking time and distance will also be measured. We will also ask the reasons for stopping or being unable to keep up with the required pace using a standardized statement and question: "You had to stop, what was it that made you stop the test?" The patients' comments were recorded verbatim.

C.10. Variable rest period. After the first and second shuttle walk test, patients will be asked to sit down and rest. How long they rest would depend on when they return to baseline level of dyspnea + 1 or below (e.g. if baseline dyspnea = 4, they need to return to a level of 5 or less to qualify for next stage) and baseline level of fatigue +1 or below. During this rest period, patients will be assessed every 5 minutes to check their dyspnea and fatigue level. If their dyspnea/fatigue level met criteria and they feel ready

to walk again, they will be given the study treatment and asked to wait for 10 minutes before they do the second walk.

C.11. Stopping rules. In the unexpected situation in which patients do not develop any increase from their baseline dyspnea after the first shuttle walk will not proceed to the next stage because of the lack of exercise-induced dyspnea. If at any time during the study patients develop chest pain, severe leg cramps, staggering, diaphoresis, and/or dizziness, they will be asked to stop the study. If patients require more than 1 hour of rest and their dyspnea and fatigue level still has not returned to baseline, they will also be taken off study. Patient dropouts and walk test failures prior to the administration of drug will be replaced.

C.12. Study assessments. See Table 5 for a detailed description of all study assessments.

Table 5. Summary of Study Assessments

Assessments	Baseline	After 1 st shuttle walk test	Rest Period	Before 2 nd shuttle walk test	After 2 nd shuttle walk test
Demographics and cancer diagnosis ¹	✓				
Medication history ²	✓				
Karnofsky performance status, spirometry testing, and inspiratory pressure ³	✓				
Edmonton Symptom Assessment Scale ⁴	✓				
Dyspnea Survey ⁵	✓				
Cancer Dyspnea Scale ⁶	✓				
O ₂ saturation and respiratory rate	✓	✓		✓	✓
Dyspnea Borg/fatigue scale ⁸	✓	✓	✓	✓	✓

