¹² patients will be asked about their dyspnea (worse, about the same, or better) comparing between the level of dyspnea between the first and second shuttle walk tests ^{53,54}. Study satisfaction will be assessed with the following questions, “Was it worthwhile for you to participate in this research study?”, “If you had to do it over, would you participate in this research study again?”, “Would you recommend participating in this research study to others?”, “Did your quality of life get better by participating in this research study?”, and “Did your quality of life get worse by participating in this research study?” Blinding will be assessed by asking patients and study staff which group assignment they believe they received: “high dose”, “low dose”, or “do not know”.

C.13. Feasibility data. In addition to clinical outcomes, we will also collect feasibility data in this study, including the following:

- Rates of recruitment and retention (% of subjects able to complete the study)
- Reasons for refusal and dropout
- Participant satisfaction—participants will provide an opinion regarding their satisfaction with study overall

C.14. Patient Safety, Monitoring, and Confidentiality.

During the study, both a research nurse and a research coordinator will be available to perform study assessments and provide safety monitoring. This study will be conducted right outside our Supportive Care Center, where we have additional support from multiple clinic nurses and doctors. The cardiopulmonary center is also very close. If desaturation occurs, we will put patient on supplemental oxygen, and determine if the patient becomes non-hypoxic after

a short rest. In the unexpected event in which the patient requires oxygen beyond nasal cannula or have prolonged hypoxemia at rest (>30 minutes), we will send the patient to ER for further assessment. Based on our experience conducting similar studies on exertional dyspnea in which we routinely monitor their vitals, there is a minimal risk of significant saturation with exercise. A study physician will also be available by pager to address any concerns, distress, or questions, and will attend to the patient as needed. See stopping rules above for further details.

Regulatory monitoring will be provided by the principal investigator and the Institutional Review Board (IRB). Patient confidentiality will be ensured by use of study numbers, secure storage of clinical data, and anonymous reporting.

Research-Related Injury

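### Oxygen is neither held constant across the two walks nor a condition for giving FSS, so a patient newly on oxygen can be dosed and walked again (minor)

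*Combined protocol and SAP*

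**What the plan says.** All references are to the combined protocol and SAP.

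- **Co-interventions.** Section B lists oxygen beside opioids and bronchodilators among the measures that ease dyspnea. C.8 says "patients will be advised to avoid using breakthrough opioids (for any reason) or bronchodilators for at least 2 hours prior to and during the study". Section C.9 adds: "Walking aid is allowed as long as patients keep them the same as before enrollment and during the entire study". Neither section names oxygen.
- **Entry.** Exclusion 2 in Table 2 is "Supplemental oxygen requirement >6 L per minute", so patients on lower flows may take part.
- **Oxygen during the visit.** C.14: "If desaturation occurs, we will put patient on supplemental oxygen, and determine if the patient becomes non-hypoxic after"; the sentence goes on to place that recheck following a brief rest. The limit is a patient who "requires oxygen beyond nasal cannula or have prolonged hypoxemia at rest (>30 minutes), we will send the patient to ER for further assessment". The same section says "there is a minimal risk of significant saturation with exercise" (desaturation is evidently meant).
- **Release to FSS.** C.10 requires dyspnea and fatigue to be within 1 point of baseline and the patient to feel ready. FSS follows, then a 10-minute wait and Walk 2. The symptoms that end participation in C.11 do not include desaturation or newly started oxygen.
- **Measurement.** C.9 schedules "oxygen saturation before and immediate after the shuttle walk test". The saturation row of Table 5 is ticked at baseline, after Walk 1, before Walk 2 and after Walk 2, and is blank for the rest period. No row or footnote lists oxygen device or flow. The medication history (footnote 2) is taken at baseline only and does not name oxygen.
- **Analysis.** D.1 bases the effect size on the within-patient change from Walk 1 to Walk 2, with 15 patients per arm. Both arms receive FSS. Section D does not mention oxygen.

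**The concern.** The plan treats Walk 1 as each patient's own control, so conditions that affect breathlessness should match in both walks except for FSS. It applies that reasoning to rescue opioids, bronchodilators and walking aids. It does not apply it to oxygen, which its own background lists as a treatment for dyspnea and which its own safety section can introduce between the walks.

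Two things are at stake. First, with no arm without FSS, a Walk 2 improvement due to added oxygen cannot be told apart from one due to the drug, and Table 5 would not show that the oxygen had changed. The test ends for the patient "when he or she was too breathless to maintain the required speed", so part of any oxygen benefit may appear as extra distance, a secondary endpoint, rather than as a lower end-of-walk Borg score. Second, a patient who has just desaturated may be given fentanyl under a release rule that contains no saturation or oxygen condition.

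**Working it through.** **1. The plan's own figure.** Inputs from D.1: n = 15, effect size 0.778, two-sided paired t-test at 0.05. With 14 degrees of freedom and noncentrality 0.778 × √15 = 3.01, exact power is 79.998%. The stated 80% is reproduced, and nothing below changes it.

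**2. Following one patient through the text.**

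| Step | Governing text | Oxygen or saturation condition? |
|---|---|---|
| Low saturation found after Walk 1 | C.9, Table 5 | Reading taken |
| Oxygen started, recheck after a short rest | C.14 | Recheck made; no flow, weaning rule or link to dosing |
| Sent to the ER | C.14 | Only beyond nasal cannula, or over 30 minutes hypoxemic at rest |
| Taken off study | C.11 | None |
| Released to FSS | C.10 | None |
| Reading before Walk 2 | C.9, Table 5 | Timed to the walk, which starts 10 minutes after FSS; no action attached |

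The reading before Walk 2 need not come before FSS. Table 5 puts FSS adverse effects in that same column, which suggests, without settling it, that the column falls after dosing. A patient comfortable on nasal oxygen can thus reach FSS and Walk 2 with every written rule met.

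**3. Direction.** Saturation is scheduled before and just after each walk, not during it. A Walk 1 desaturation would therefore normally be found once the distance is fixed and at about the time of the end-of-walk Borg rating. Oxygen started then and kept on helps only Walk 2, which favors FSS.

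**4. Size.** The documents give neither the Borg effect of oxygen nor the SD of the change. Assumptions: effect e = 1 point (the plan's minimal important difference for Borg, from COPD), range 0.5 to 2; SD 1.5, range 1.0 to 2.5.

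- Shift in an arm mean = (k/15) × e, where k is the number of affected patients. For k = 1: 1/15 × 1 = 0.067, range 0.5/15 = 0.033 to 2/15 = 0.133.
- 95% half-width = t(0.975, 14) × SD/√15 = 2.145/3.873 × SD = 0.554 × SD, which is 0.55, 0.83 and 1.38 at SD 1.0, 1.5 and 2.5.
- Ratio for one patient: 0.067/0.831 = 8%, range 0.033/1.384 = 2.4% to 0.133/0.554 = 24%.
- Stress case: k = 3, e = 2 gives 3/15 × 2 = 0.40, or 0.40/0.83 = 48% of the half-width at SD 1.5. With no true FSS effect, the chance of a significant paired test would then rise from 5% to 16.1%.

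**5. Frequency.** The documents give no rate. For assumed rates p of 1%, 2% and 5%:

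| p | Expected number of 30 | Chance of at least one: 1 − (1 − p)^30 | Expected bias p × e, e = 1 |
|---|---|---|---|
| 1% | 0.3 | 26% | 0.01 |
| 2% | 0.6 | 45% | 0.02 |
| 5% | 1.5 | 79% | 0.05 |

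At the upper end (p = 5%, e = 2) the expected bias is 0.10 Borg. The smallest standard error considered, at SD 1.0, is 1/3.873 = 0.26.

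**The case against.** The strongest reply is that C.14 already deals with desaturation. Staff recheck after a short rest, the 30-minute hypoxemia rule implies continued readings, a nurse and a coordinator monitor the patient, and a physician is on call. A reader might infer from the blank rest-period cell that nobody looks at saturation between Walk 1 and FSS. The documents do not support that: there is a reading after Walk 1, and the C.14 recheck would fall in the rest period. What remains is narrower. The recheck is not a condition for dosing, and it does not say whether the patient must be off the added oxygen.

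A reader might also infer that the bias could as easily run against FSS. That would need oxygen given during Walk 1 and then removed, or a patient changing their own flow. The plan schedules neither, so the reverse direction is possible but secondary.

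C.9 defers to published walk procedures, and C.6 provides staff orientation. Those procedures are not in the documents; if they fix oxygen, the protocol need only say so. Table 5 is a summary and no case report form is available, so one cannot conclude that flow goes unrecorded, only that the plan does not list it.

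Finally, the plan regards the risk as minimal, and the missing no-FSS arm is the larger limitation. Both points stand, and they are why this is minor. Oxygen is, however, a part of that limitation that can be removed without redesign.

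**Conclusion.** The point holds as a minor one. As written, the plan lets a patient who desaturates after Walk 1 receive fentanyl and repeat the walk on added oxygen, with no saturation or oxygen condition on dosing and no listed record of the change. This would mainly flatter FSS in the within-arm change.

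The size rests on assumed values for the oxygen effect, the SD and the rate. One affected patient moves an arm mean by about 0.07 Borg (0.03 to 0.13), and the expected bias is below sampling error across the assumed rates. It would be wrong to infer that the pilot's effect size is unusable. It would also be wrong to extend the point to the randomized high-versus-low comparison (objective A.3), which is affected only if oxygen changes differ by arm; nothing in the documents says that they will. The case for acting rests on an interpretable pair of walks and a safety check before fentanyl, not on a large numerical bias.

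**What to change.** 1. **C.9.** Extend the walking-aid sentence to oxygen: same device and flow in both walks, as at the start of Walk 1, never withholding oxygen that is needed. If the cited procedures already require this, state it.
2. **C.10.** Take one saturation and flow reading just before FSS. Dose only if the patient is on the Walk 1 setting and saturation is within a pre-set margin of the resting value before Walk 1 (for example 2 to 3 points, an assumption for the investigators to set). Do not dose if oxygen was started or raised during Walk 1, since returning to the starting setting would then leave Walk 2 with less oxygen than Walk 1, or if the patient cannot be returned to the Walk 1 setting.
3. **C.11.** Name these patients as pre-drug failures to be replaced. The current replacement sentence does not clearly cover them, although C.4 already has a mechanism for replacing someone who does not take the study drug.
4. **Table 5 and D.2.** Record device and flow wherever saturation is recorded, including the new pre-dose reading. List any dosed patient whose oxygen changed, including after FSS, and keep all dosed patients in the primary estimate.

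The cost is a sentence or two in each of C.9, C.10 and C.11, one data field, one pulse-oximeter reading and one listing. The downside is that a few patients who desaturate may be replaced, which makes the sample slightly less representative and may slightly lengthen accrual.

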A Preliminary Study of Prophylactic Fentanyl Sublingual Spray (FSS) for Exercise-Induced Breakthrough Dyspnea

Principal investigator: [name]

Supportive Care Co-investigator: [name]

Collaborators: [name], [name]

Table of Contents

A. Study Objectives	2
B. Background.....	2
C. Experimental Approach	2
D. Statistical Analysis	12
E. Data Confidentiality Procedures.....	13
F. References.....	14

A. Study Objectives

Primary objective:

To determine the **effect of prophylactic fentanyl sublingual spray** (FSS, 15-25% and 35-45% proportional doses) on the **intensity of exercise-induced dyspnea** (modified Borg scale) between the first and second shuttle walk tests. *We aim to estimate the effect size for both FSS arms to inform a larger, adequately powered confirmatory randomized controlled trial.*

Secondary objectives

A.2. To determine the **effect of prophylactic FSS** (15-25% and 35-45% proportional doses) on **walk distance and adverse effects** between the first and second shuttle walk tests. *We hypothesize that FSS is superior to no FSS in increasing walk distance and has limited side effects in opioid tolerant individuals.*

A.3. To compare the **intensity of exercise-induced breakthrough dyspnea** between high (35-45% proportional dose) and low (15-25% proportional dose) doses of prophylactic FSS. *We hypothesize that higher doses of FSS is superior to lower doses FSS in reducing dyspnea at the end of the shuttle walk test.*

B. Background

Dyspnea is a subjective awareness of difficulty breathing, which may be associated with the distressing sensation of suffocation. It is one of the most common and most feared symptoms among cancer patients, occurring in up to 70% of patients in the last 6 weeks of life ^{1,2}. Dyspnea is associated with fatigue, anxiety, decreased function and quality of life, and increased mortality ^{3,4}.

In a study examining 70 patients with dyspnea, 43 (61%) reported breakthrough (episodic or incidental) dyspnea only, 13 (19%) had constant dyspnea only, and 14 (20%) experienced both constant and breakthrough dyspnea. A substantial proportion of the patients with breakthrough dyspnea (18/57, 32%) presented with 5 or more episodes per day, and the majority of episodes lasted <10 minutes ⁵. Breakthrough dyspnea is particularly challenging to treat because of its transient and episodic nature.

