Fentanyl sublingual spray (FSS) is a particularly attractive option for breakthrough dyspnea. It was approved by the US Food and Drugs Administration in 2012 for “the management of breakthrough pain in adult cancer patients who are already receiving and who are tolerant to around-the-clock opioid therapy for their underlying persistent cancer pain”, and represents an alternative delivery system for fentanyl that also utilizes a transmucosal route like OTFC. A pharmacokinetic study examining 5 different doses of FSS (100 mcg, 200 mcg, 400 mcg, 600 mcg, 800 mcg) in healthy volunteers demonstrated that fentanyl enters the systemic circulation rapidly, achieving 27%, 61%, 87% and close to 100% of maximal plasma concentration (Cmax) within 5, 10, 20 and 30 minutes, respectively ²⁹. In a separate crossover study comparing FSS 400 mcg, OTFC 400 mcg and intravenous fentanyl 100 mcg in healthy volunteers, FSS had a greater bioavailability (76% vs. 51%) and achieved a higher Cmax than OTFC (0.81 mg/ml vs. 0.61 ng/ml). Similar to the previous study, the mean plasma concentrations were 19% and 54% of Cmax within 5 and 10 minutes ³⁰. In a double-blind, randomized placebo controlled trial, FSS provided greater and more rapid pain relief, and significantly reduces pain compared to placebo at 5, 30 and 60 minutes ²⁸. The most common adverse effects included nausea (7%), hyperhidrosis (5%) and peripheral edema (5%).

Significance. We expect to advance the understanding of how FSS can be used to treat exertional dyspnea in cancer patients. The effective management of dyspnea may ultimately help alleviate this devastating symptom. A better fundamental understanding of how this intervention improves physiologic parameters could also shed light on the pathophysiologic characteristics of dyspnea and allow us to devise new and more effective treatments.

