⁷ a 0 to 10 categorical scale for rating the severity of dyspnea. It is a ratio scale with descriptive anchors throughout the range in which a rating of 8 signifies breathlessness twice as severe as 4, which in turn is twice as severe as 2 ⁴⁰⁻⁴³. We will be measuring it every minute during the shuttle walk test starting from 0 minutes until the end of walk. This will be the primary endpoint because it has good reliability and validity for assessing dyspnea ^{40,41,44} and has been used in multiple other studies on exertional dyspnea ⁴⁵⁻⁴⁸. The minimal clinically important difference is 1.0 in patients with chronic obstructive pulmonary disease ⁴⁹. This scale can be administered quickly, and was found to be easy to use by patients ⁴¹. In a study that compared the dyspnea modified Borg Scale, numeric rating scale and visual analog scale, the modified Borg scale was preferred by participants and was recommended as the best tool to quantify dyspnea intensity ⁵⁰. Furthermore, its use is recommended by the American Thoracic Society and American College of Chest Physicians for Cardiopulmonary Exercise Testing ⁵¹.

⁸ a 0 (no dyspnea) to 10 (worst dyspnea) categorical scale validated for rating the severity of dyspnea ^{40,42,43}. The intensity and unpleasantness of dyspnea will be measured using the Borg scale 10 minutes prior to the shuttle walk test, every minute during the shuttle walk test until the end of the walk, and immediately after each shuttle walk test

⁹ include the total distance walked, total walking time, the distance and time of first rest due to dyspnea, average walking speed.

¹⁰ adverse effects related to the use of FSS, such as dizziness, drowsiness and nausea will be assessed using a numeric rating scale from 0-10.

¹¹ patients will be asked to do a finger tapping test, simple math test, reverse memory of digits, and visual memory). This has been used in other studies by our group. ⁵²

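### The last scheduled saturation and respiratory rate readings fall about 10 to 22 minutes after FSS, right after exertion; one seated reading near the 30-minute peak would be a cheap addition

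*Combined protocol and SAP*

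**What the plan says.** Section C.9 fixes the interval between dose and exercise: "The second shuttle walk test will be conducted 10 minutes after study medication has been administered". It then places the vital signs: "We will also measure the heart rate, respiratory rate, blood pressure, oxygen saturation before and immediate after the shuttle walk test". Table 5 agrees. Saturation and respiratory rate are ticked at Baseline, after the first walk, before the second walk and after the second walk. The Rest Period cell is blank, and there is no later column.

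The Background describes a study in healthy volunteers in which sublingual fentanyl entered the circulation quickly, "achieving 27%, 61%, 87% and close to 100% of maximal plasma concentration (Cmax) within 5, 10, 20 and 30 minutes, respectively".

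Section C.10 has patients sit and rest after both walks, for as long as dyspnea and fatigue need to settle: "During this rest period, patients will be assessed every 5 minutes to check their dyspnea and fatigue level". It mentions no other measurement.

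Section C.14 has a research nurse and a coordinator on hand for safety monitoring and a physician on call by pager. On hypoxemia it says "If desaturation occurs, we will put patient on supplemental oxygen, and determine if the patient becomes non-hypoxic after" a brief rest, with transfer to the ER if more than nasal cannula is needed or if hypoxemia at rest lasts over 30 minutes. It adds that "there is a minimal risk of significant saturation with exercise".

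Adverse effects are part of secondary objective A.2, whose hypothesis is that FSS "has limited side effects in opioid tolerant individuals". Table 5 footnote 10 describes how they are captured: "adverse effects related to the use of FSS, such as dizziness, drowsiness and nausea will be assessed using a numeric rating scale from 0-10". Table 5 ticks these ratings before and after the second walk and gives no minute.

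**The concern.** The study gives a single opioid dose of up to 1000 mcg (Table 3, high-dose arm, for patients on 401-500 mg MEDD). On the schedule as written, the last respiratory measurement is taken while plasma levels are still rising and while the patient has just been walking. Effects of exertion and drug are mixed in that value. Saturation or respiratory rate that falls later, when the patient is seated and the drug is near its peak, has no scheduled reading that would record it.

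The protocol itself makes respiratory rate relevant. Three of the case series in its Table 1, using transmucosal or intranasal fentanyl, report that it fell, although they report this alongside benefit and not as harm. The pilot is meant to inform a larger trial, so a by-arm respiratory value near peak would be useful to have. Without one, any statement about respiratory safety covers only the earlier window.

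**Working it through.** **Inputs**
- Dose to start of second walk: 10 minutes (C.9, C.10).
- Walk length: at most 12 levels of 60 seconds (Table 4). The shortest case taken is a test ended at the first 20-second shuttle.
- Vital signs: immediately after the walk (C.9).
- Concentration: 27%, 61%, 87% and about 100% of Cmax at 5, 10, 20 and 30 minutes (Background).
- Rest checks: every 5 minutes (C.10), with the first assumed to come 5 minutes after the walk ends.

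**The plan's own figures.** Table 4 reproduces: shuttles of 3 to 14 per level sum to 102, and 102 × 10 m = 1020 m over 12 minutes. The power statement in D.1 also reproduces (paired t-test, n = 15, standardized effect 0.778, two-sided 0.05: 79.998%). Nothing below depends on it.

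**Time of the last reading** = 10 minutes + walk time. Percentage of Cmax by linear interpolation (an assumption) is 61 + 2.6 × (t − 10) up to 20 minutes and 87 + 1.3 × (t − 20) after that.

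| Walk time | Last reading post-dose | % of Cmax, linear | Minutes before 30 |
|---|---|---|---|
| 20 s | 10.33 min | 61.9 | 19.7 |
| 4 min | 14 min | 71.4 | 16 |
| 6 min | 16 min | 76.6 | 14 |
| 12 min | 22 min | 89.6 | 8 |

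**Direction of error.** The curve flattens: 34/5 = 6.8 points per minute from 5 to 10 minutes, then 26/10 = 2.6, then 13/10 = 1.3. Straight lines therefore run low between the reported points. If the curve is concave throughout, extending the neighbouring segments gives upper bounds:
- 14 minutes: 87 − 1.3 × 6 = 79.2%
- 16 minutes: 87 − 1.3 × 4 = 81.8%
- 22 minutes: 87 + 2.6 × 2 = 92.2%

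So the linear figures are at the low end, but on either reckoning the last value precedes the 30-minute point. In the other direction, the second pharmacokinetic study in the Background gives 54% at 10 minutes, not 61%.

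**First rest check** = last reading + 5 minutes = 15.33 to 27 minutes post-dose. It falls before 30 minutes for any walk length and includes no saturation or respiratory rate.

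**The reading before the second walk.** The documents do not say whether it is taken at dosing or after the wait. At the latest it is at 10 minutes.

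**What an added reading could show.** With zero events, the exact two-sided 95% upper limit is 1 − 0.025^(1/n). For 0/15 this is 1 − 0.025^(1/15) = 21.8%. For 0/30 it is 1 − 0.025^(1/30) = 11.6%.

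**The case against.** The case against giving this much weight is good, and most of it stands.

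First, a reader might infer that the plan leaves later hypoxemia unattended. It does not. C.14 responds to desaturation whenever it is noticed and is not restricted to the end of the walk. Its provision for prolonged hypoxemia at rest presupposes repeat readings at rest. What is missing is a scheduled, recorded value, not a clinical response. The low-risk remark in C.14 concerns exercise, so it does not settle the matter for seated rest.

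Second, a reader might infer that patients go home at the first rest check, 15 to 27 minutes post-dose. No section says so. Table 5 also lists adverse effects, neurocognitive testing, global assessment, satisfaction and blinding after the second walk, and these probably keep patients on site longer. No vital sign is tied to them.

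Third, a reader might infer that A.2 draws a respiratory conclusion the data cannot bear. A.2 and footnote 10 speak of side effects and name dizziness, drowsiness and nausea as examples. Saturation and respiratory rate form a separate row of Table 5, and no respiratory conclusion is stated. The end-of-walk readings suit the comparison that D.2 describes, first walk against second at the same moment. A seated 30-minute value would have no counterpart after the first walk and could be compared only with Baseline.

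Fourth, dosing is proportional in opioid-tolerant patients, so the 1000 mcg figure should not be read without the MEDD that goes with it. Nor do the documents show that respiratory effect follows plasma concentration.

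None of this supplies a scheduled respiratory value near 30 minutes.

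**Conclusion.** The point holds as a minor, inexpensive improvement to the assessment schedule. The last scheduled saturation and respiratory rate readings fall about 10 to 22 minutes after FSS, immediately after exertion and 8 to 20 minutes before the time at which the protocol's own source puts plasma levels close to maximum. No minimum observation time after the dose is stated. No analysis is in error, and the primary endpoint and the power statement are untouched.

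The timing range rests only on C.9, C.10 and Tables 4 and 5. The percentages of Cmax rest on interpolation of healthy-volunteer data and are probably somewhat low. The documents give no size for a saturation effect, so none is claimed. Figure 1 and the appendix with the walk instructions are not available here, so a reading listed only there cannot be ruled out.

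**What to change.** Add one seated saturation and respiratory rate reading at about 30 minutes after the dose, together with the footnote 10 ratings, within the existing rest and assessments after the second walk. Keep patients until it is done. State also that the readings before the second walk are taken at the end of the 10-minute wait.

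Report the new values by arm, descriptively, as change from Baseline, with the number of patients needing the C.14 oxygen or ER steps and exact 95% confidence intervals. Say alongside them that residual exertion and the absence of a placebo arm limit attribution, and that 15 patients per arm allow description only.

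The cost is one brief assessment, 8 to 20 minutes after the end-of-walk vital signs, by staff already present. Patients who recover quickly may wait a few extra minutes in a visit of about 2 hours. It adds one table and no patients. If the reading is not added, limit any statement about respiratory safety to the roughly 10 to 22 minutes post-dose that were observed.
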